3.4.4 Study Outcomes and Definitions

[figure not shown]
The primary outcome of interest is the off label use of Byetta in Canada.

A patient's therapy type will be inferred by identifying if a patient switches between, or adds on to therapies, as shown in figure 3.

Mono Therapy is defined as a patient receiving a specific therapy (Therapy 1) prior to a different therapy (Therapy 2) where Therapy 1 is not detected after Therapy 2 initiation. Mono therapy for this study, refers to a patient received a prescription for only one product at a given time.

Concomitant Therapy is defined as a patient receiving a specific therapy (Therapy 1) prior to a different therapy (Therapy 2) where Therapy 1 is detected after Therapy 2 initiation.

Figure 3: Distinguishing between add-on and switch therapies

Patients will be selected for the study if they receive a Byetta script anytime during the analysis period and if they met the inclusion criteria. To identify on-label vs. off-label use, patient history will then be used to classify patients as "inferred on-label" if they also received Metformin and/or SU or Lantus during the study (Business rules 1 and 2 in Table 5).

All other patients that do not meet the criteria for use of Byetta with metformin and/or SU or Lantus will be classified as “inferred off-label”. The group of patients classified as “inferred off-label” will then be further classified to gain a better understanding of the trends in “inferred off-label” use of Byetta (Business rules 3-10 in Table 5).

The Business rules described in Table 5 are prioritized to ensure the appropriate classification of each patient. Therefore patients will be classified based on the highest rank business rule. For example, if a patient receives scripts for both Metformin and other insulin during the analysis period, they will be classified as “inferred on-label” as they have a script for metformin and therefore are classified by business rules 1 and 2

Note: The patient classification categories (‘Inferred Adherence Label’) can be modified in the initial phase of the project.

Table 5: Business rules applied to classify patients as “on-label” vs. “off-label”

(The business rules have been structured to align with the Canada monograph for Byetta indication and clinical use (see Table 1) and will be finalized upon study initiation).

Rank	Business Rules	Cohort Description	Inferred Adherence Label
1	Concomitant use of* Byetta with metformin (met) and/or sulfonylurea (SU), OR Concomitant use of Byetta with Lantus	Met and/or SU or Lantus is prescribed with Byetta	Inferred On-label
2	Evidence of** Byetta and metformin and/or sulfonylurea OR Evidence of Byetta and Lantus	Met and/or SU or Lantus is not prescribed with Byetta, but both appear in the analysis period	Inferred On-label
3	Evidence of Byetta and Levemir	Levemir is prescribed in the analysis period	Off-Label Insulin Use
4	Evidence of Byetta and Human Basal Insulin	Human basal insulin is prescribed in the analysis period	
5	Evidence of Byetta and thiazolidinedione (TZD)	TZD is prescribed in the analysis period	Off-Label OAD Use

6	Byetta Alone	No other products prescribed in the analysis period	Inferred Off-label
7	Evidence of Byetta and all other insulin	Other insulin is prescribed in the analysis period	
8	Evidence of Byetta and all other OADs	Other OADs are prescribed in the analysis period	
9	Pediatric Patients	Patient is under the age of 18 (<18)	
10	All other combinations	All other combinations	

Note: Evidence of Diabetic ketoacidosis, diabetic coma/precoma and end stage renal disease cannot be inferred from the dataset; therefore we will not be able to identify these patients as a separate group

* "Concomitant use of..." refers to continued use of Byetta and other product

** "Evidence of..." refers to anytime within the study period including look-back or look forward periods

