3.2.2 Secondary Objective

To assess the concomitant use of exenatide with either thiazolidinediones (TZDs) or insulin.

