3.4.2 Study Design

This will be a retrospective database study using IMS Brogan's LRx dataset, in which de-identified patient level prescription information will be used to evaluate adherence to the labeling recommendations for exenatide use in Canada. The study will be based on a 'Look-Back,' 'Analysis' and 'Follow-Up' period as shown in figure 1. Patients will be selected for the study if they are receiving a Byetta prescription in the 12 month analysis period.

[figure not shown]
The 'Look-back' period is used to ensure that each patient within the analysis period has at least 6 months of data prior to first Byetta script. This eligibility period ensures that a patient whose first Byetta script occurs at the start of the analysis period can be classified appropriately and that they are present in the database prior to the first script. Similarly, the 'Follow-up' period is used to ensure that each patient has at least 3 months of data following the last script within the analysis period. This ensures that the duration of therapy for a patient who receives their last script at the end of the analysis period is accounted for and can have their therapy appropriately classified, specifically around the concomitant use of Byetta with insulin or TZDs.

Figure 1: Study periods proposed for analysis of Byetta use in the 1st year post launch

In addition to the study period proposed in figure 1, the analysis will be conducted for Year 1, 2 and 3 post Byetta launch allowing for an analysis of trends in Byetta use over time, as shown in figure 2. Study 1* will provide results on Year 1 and 2 and would commence at the availability of Aug 2013 data. Study 2** will provide Year 3 results and would commence at the availability of Aug 2014 data.

Figure 2: Three proposed analysis periods for study post Byetta Launch

Note: Implies that the look-back period and the follow-up period are at least 6 months and 3 months for each patient, respectively.

Note: Month 1 = Date of First Byetta Sale = June 2011

*Study 1: All Byetta prescriptions in the database in months 0-24, post launch

** Study 2: All Byetta prescriptions in the database in months 25-36, post launch

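### The written definition of concomitant therapy counts a patient who stopped Byetta and went back to insulin or a TZD as a co-user, so sequential use can be reported as concomitant use

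*Protocol*

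**What the plan says.** Protocol section 3.4.4 infers therapy type from the order of scripts. In both definitions Therapy 1 comes before Therapy 2.

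- Concomitant therapy is the case "where Therapy 1 is detected after Therapy 2 initiation".
- Mono therapy is the case "where Therapy 1 is not detected after Therapy 2 initiation". A second sentence adds that, for this study, mono therapy "refers to a patient received a prescription for only one product at a given time".
- The single-asterisk footnote to Table 5 says that concomitant use "refers to continued use of Byetta and other product". The asterisk stands at business rule 1 (metformin, sulfonylurea, Lantus).
- The double-asterisk footnote says that *evidence of* use, the wording of rules 2-5, 7 and 8, "refers to anytime within the study period including look-back or look forward periods".

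The secondary objective in section 3.2.2 is "To assess the concomitant use of exenatide with either thiazolidinediones (TZDs) or insulin". Section 3.4.2 justifies the follow-up period by the need to classify therapy, "specifically around the concomitant use of Byetta with insulin or TZDs". Table 7 in section 3.4.6 is a table of concomitant medications with rows for TZD and insulin. It does not say which definition fills it.

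**The concern.** The concomitant rule looks only at whether the earlier drug reappears after the later one starts. It does not ask whether the later drug is still being filled, whether the two overlap in time, or whether there is more than one script. Two kinds of patient without sustained joint use are therefore concomitant: one who abandons Byetta and resumes the earlier drug, and one who switches to Byetta but collects a single late refill of the earlier drug.

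Section 3.1 reports that the regulator asked specifically about use with a TZD or insulin, and the secondary objective exists to answer that. The follow-up requirement, that "each patient has at least 3 months of data following the last script within the analysis period", opens the window in which a return to the earlier drug can be seen. The rule then reads that return as co-use. For these histories the error runs in one direction only, towards more reported co-use.

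**Working it through.** The protocol states no rate or sample size to reproduce, so the check applies the written rule to model histories. X is insulin or a TZD, scripts are monthly, and Byetta starts at month 0. The last column counts X scripts dated from the first to the last Byetta script, as a simple reading of continued use of both.

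| History | X scripts (months) | Byetta scripts (months) | Section 3.4.4 rule | X scripts while Byetta continues |
|---|---|---|---|---|
| Add-on | -6 to 9 | 0 to 9 | concomitant | 10 |
| Clean switch | -6 to -1 | 0 to 9 | mono | 0 |
| Switch-back | -6 to -1, then 5 to 9 | 0 to 3 | concomitant | 0 |
| One late refill | -6 to -1, then 0.5 | 0 to 9 | concomitant | 1 |
| Byetta stopped, X then first started | 5 to 9 | 0 to 4 | mono | 0 |
| Same-day start | 0 to 9 | 0 to 9 | not covered | 10 |

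Three things follow.

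1. The switch-back patient is concomitant with no X script during Byetta use. The same patient fits the one-product-at-a-time description of mono therapy and fails the continued-use footnote. A programmer cannot satisfy all three texts.
2. Rows 3 and 5 both show no joint use, yet they are classified in opposite ways. The only reason is that X was used before Byetta in one and not in the other.
3. The same-day starter has ten joint scripts but is neither mono nor concomitant, because neither drug came first.

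**Which outputs move.** A metformin, sulfonylurea or Lantus patient who is not concomitant under rule 1 meets rule 2 through the *evidence of* footnote, and rule 2 carries the same inferred on-label status. Rules 3-5 and 7, which cover Levemir, human basal insulin, TZD and other insulin, need only evidence of use at any time in the study period. The on-label/off-label split and the off-label categories therefore do not depend on the concomitant definition. What depends on it is the secondary objective, Table 7 if that table uses it, and the split between rules 1 and 2. Neither Table 6 nor Table 7 reports that last split.

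**Illustrative size.** Let c be the true concomitant share and s the share of patients who return to the earlier drug after stopping Byetta, both as fractions of all Byetta patients and not overlapping. Then reported share = c + s and relative overstatement = s / c. The protocol gives neither value, so both ranges are assumptions: c from 5% to 20%, s from 2% to 10%.

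- Lowest reported share: 5% + 2% = 7%. Highest: 20% + 10% = 30%.
- Smallest relative overstatement: 2 / 20 = 10%. Largest: 10 / 5 = 200%.
- Middle case: c = 10%, s = 5% gives 15%, an overstatement of 5 / 10 = 50%.

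**The case against.** The best defence is that the plan clearly intends overlap. Section 3.4.4 refers to Figure 3 for the distinction between add-on and switch, the figure is not available in the text reviewed, and it may depict overlap. The one-product-at-a-time sentence and the continued-use footnote point the same way. The business rules are to be finalised at study start, and refill and gap conventions are commonly left to a statistical analysis plan.

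This shows what was meant but does not repair the rule as written. The text gives an explicit test, and that test returns the wrong class for a foreseeable history. That is a misstated rule and not an omitted detail. If Figure 3 does show overlap, the text still has to be brought into line with it. The note about finalising rules is attached to Table 5, not to the therapy definitions.

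Two further points on the other side stand, and they limit the concern:

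- The asterisk for continued use is attached only to rule 1. For a TZD or insulin other than Lantus, the conflict with the footnote is indirect: one term carries two meanings, and section 3.4.4 holds the only definition that reaches those drugs.
- A reader might infer that a late metformin refill inflates on-label use, or that switch-back inflates the off-label insulin and TZD categories. The documents do not support either reading, because rule 2 and the *evidence of* rules assign those labels without any test of concomitancy.

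**Conclusion.** The concern holds for the secondary objective and not for the primary outcome. As written, section 3.4.4 counts switch-back and single-refill patients as concomitant and leaves same-day starters unclassified, against its own mono-therapy wording and the sense of the Table 5 footnote. If followed, it reports sequential use of insulin or a TZD as co-use with Byetta. How often this happens cannot be computed from the protocol. The range of 10% to 200% rests wholly on assumed shares and shows only that the error could be small or could dominate the estimate. The effect on Table 7 is conditional on that table using the section 3.4.4 definition. The definition should be corrected before the classification is programmed.

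**What to change.** Use one script-date definition in section 3.4.4, Table 5 and Table 7:

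- A partner drug is concomitant if it has at least two scripts dated on or after the first Byetta script, and the first of these is dated on or before the last Byetta script.
- Same-day starts are judged by the same rule.
- Patients whose partner scripts resume or begin only after the last Byetta script are reported as switch-back or switch.
- Patients with a single trailing partner refill, or with only one Byetta script, are shown separately.
- Figure 3 is checked against this text.

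On the six histories, the add-on and same-day starters are concomitant, the two plain switches and the switch-back patient are not, and the late-refill patient goes to the separate group. The second script must be of the partner drug. If a later Byetta script could serve, the lone late refill would count as co-use again.

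The cost is a wording change and slightly more programming, on script dates already held. Some true overlap within the last Byetta supply will fall into the separately shown groups. Two mixed histories would still count as concomitant: one late partner refill followed by a return to that drug after Byetta ends, and a run of the partner drug inside an interruption of Byetta. Both can be flagged from the same dates.

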3.1 Rationale

Exenatide is an injectable glucagon-like peptide 1 (GLP-1) receptor agonist approved as an adjunct to diet and exercise to improve glycemic control in adults with type 2 diabetes mellitus (T2DM) by the United States and Europe. Byetta (exenatide twice daily) is administered as a subcutaneous injection within 1 hour before the two main meals of the day, approximately 6 hours or more apart. Treatment is typically initiated at 5 mcg per dose, twice daily, and may be increased to 10 mcg twice daily based on the patient’s clinical response.

During Health Canada’s review of the marketing authorisation application of exenatide, Lilly provided a commitment to monitor the off-label use and compliance to the Summary of Product Characteristics (SPC) of exenatide prescriptions through a post-launch utilization study. Specifically, Health Canada requested that:

The RMP should be revised to include a post-marketing study conducted on exenatide use and adherence to labeling recommendations in Canada, similar to the drug utilization study requested by the EU Regulatory authority that is currently ongoing in various EU countries. Since preliminary information has already indicated off label use of exenatide with either TZD or insulin in the EU, the need for further study and/or additional risk management actions with these products should be specifically addressed.

Table 1: Canadian Byetta Indication

Byetta Monograph
Indication and Clinical Use:
BYETTA is indicated in combination with metformin and/or sulfonylurea to improve glycemic control in patients with type 2 diabetes mellitus, when maximally tolerated doses of these oral therapies in addition to diet and exercise do not provide adequate glycemic control.
BYETTA is indicated in combination with insulin glargine (with or without metformin) to improve glycemic control in patients with type 2 diabetes mellitus when insulin glargine (with or without metformin) in addition to diet and exercise, does not provide adequate glycemic control
Contraindication:
BYETTA should not be used in the pediatric patient population.

BYETTA should not be used in patients with end-stage renal disease or severe renal impairment (creatinine clearance <30 mL/min), including patients receiving dialysis

BYETTA is contraindicated in patients with diabetic ketoacidosis, diabetic coma/precoma or type 1 diabetes mellitus.

Source: Byetta Drug Product Monograph, Canadian Pharmacists Association, online version, April 2011.

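### Ranks 1 and 2 do not require metformin, SU or Lantus to precede Byetta, so patients who start Byetta first or simultaneously count as inferred on-label

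*Protocol*

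**What the plan says.** Table 1 (section 3.1) gives two indications. With metformin and/or a sulfonylurea, Byetta is for use "when maximally tolerated doses of these oral therapies in addition to diet and exercise do not provide adequate glycemic control". With insulin glargine, it is for use when glargine, with or without metformin, "in addition to diet and exercise, does not provide adequate glycemic control". Section 3.4.4 states that the Table 5 rules were built to match this monograph.

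The text of section 3.4.4 makes a patient inferred on-label "if they also received Metformin and/or SU or Lantus during the study". Table 5 carries this out in two ranks:

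- Rank 1 is "Concomitant use of* Byetta with metformin (met) and/or sulfonylurea (SU), OR Concomitant use of Byetta with Lantus". Its footnote says that the term "refers to continued use of Byetta and other product". Section 3.4.4 separately defines Concomitant Therapy as Therapy 1 given before Therapy 2, "where Therapy 1 is detected after Therapy 2 initiation".
- Rank 2 covers patients for whom "Met and/or SU or Lantus is not prescribed with Byetta, but both appear in the analysis period". The footnote to *Evidence of* is wider still and takes in the look-back and look-forward periods.

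The highest-ranked rule that fits decides the class, so Ranks 1 and 2 override every off-label rule. Section 3.4.2 requires at least 6 months of data before the first Byetta script and says of it: "This eligibility period ensures that a patient whose first Byetta script occurs at the start of the analysis period can be classified appropriately". Section 3.4.7 says that off-label use is probably over-estimated because the on-label rules are strict.

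**The concern.** Both indications presuppose that the partner therapy is already in use and is not enough. A rule meant to mirror them should ask whether metformin, SU or Lantus was dispensed before Byetta. Pharmacy data can show this, unlike dose adequacy or glycaemic control. The protocol secures the look-back that the check needs, but no on-label rule uses it for this purpose.

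The primary objective is use outside the labelled indication, in a study that answers a Health Canada request. If a detectable sequence that the indication does not cover is counted as adherent, the off-label share is too low by the size of that group. A reader of section 3.4.7 would assume the opposite direction.

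**Working it through.** The protocol states no figure that bears on this point, so the check traces each drug order through Table 5. *Partner* means metformin, SU or Lantus.

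| Order | Rule met | Class |
|---|---|---|
| (a) Partner first, Byetta added, both continued | Rank 1 | On-label |
| (b) Byetta first, partner added later, both continued | Rank 1 if Byetta may be Therapy 1, otherwise Rank 2 | On-label |
| (c) Both first filled on the same day | Rank 1 by its footnote, otherwise Rank 2 | On-label |
| (d) Byetta stopped, partner first filled later in the study period | Rank 2 | On-label |
| (e) Partner stopped, then Byetta without it | Rank 2 | On-label |

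Order (a) fits the add-on sequence in Table 1. Orders (b), (c) and (d) do not, because no partner drug came before Byetta. Order (e) has the right sequence but no combination use. It is a related matter and affects only how lapsed fills are assigned.

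**Can a later rule correct this?** No. Ranks 3 to 10 apply only to patients who fail Ranks 1 and 2.

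**Do the Table 3 exclusions remove these patients?** No. The consistent-patient criterion asks for some earlier prescription at the store, not a diabetes prescription. The 12-month-gap criterion concerns gaps between diabetes prescriptions. The look-back criterion asks for 6 months of data, not 6 months of diabetes therapy. A patient with other prescriptions but no earlier diabetes drug stays in.

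**Is the result consistent with the rest of Table 5?** Not fully. Rank 6 treats Byetta alone as off-label, yet a patient who starts that way becomes on-label by filling metformin later. The time available for that later fill depends on the start date. With a 12-month analysis period and the minimum 3-month follow-up, a patient starting on the first day has 12 + 3 = 15 months, and one starting on the last day has 3.

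**Size.** Let *q* be the off-label share under the current rules and *f* the fraction of inferred on-label patients with no partner fill before Byetta. If that group is taken out of the on-label count, the share not on-label is

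q + f(1 − q).

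The documents give neither *q* nor *f*. Purely as arithmetic, assume q = 20%:

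- f = 0: 20%
- f = 5%: 0.20 + 0.05 × 0.80 = 24%
- f = 10%: 0.20 + 0.10 × 0.80 = 28%
- f = 20%: 0.20 + 0.20 × 0.80 = 36%

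These values show how the share responds to *f*. They do not predict it.

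**The case against.** Several points on the other side have force.

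*Rank 1 is not free of order.* Concomitant Therapy is defined by sequence, and its purpose is to separate add-on from switch. Figure 3, which illustrates it, is not available. One may read Therapy 1 as the background drug and Therapy 2 as Byetta. This stands as a possible reading, so a reader should not infer that Rank 1 ignores sequence altogether. It does not rescue the classification, because Rank 2 takes in every order that Rank 1 would then reject. For the same reason it does not matter whether same-day starters fall under Rank 1 or Rank 2.

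*Order is only a proxy.* An earlier fill does not show that the dose was maximal or that control was inadequate. The absence of one does not show that the patient was untreated: LRx covers 74.6% of national prescription volume and only 53.1% in Newfoundland / PEI, and Table 3 itself recognises that patients use more than one pharmacy. This stands. It argues for a separate, neutrally named row and against declaring these patients off-label.

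*The regulator named TZD and insulin use.* True. A reader might infer that first-line Byetta is a main form of off-label use, but the protocol does not say so.

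*The rules are labelled as inferred and are to be finalized at study initiation.* This makes the change easy. It does not commit the study to making it, and section 3.4.7 does not disclose the gap.

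**Conclusion.** The point holds as a defect in the definition of the primary outcome. As written, Ranks 1 and 2 together count patients as inferred on-label whichever drug came first, while Table 1 describes an add-on. The effect on the off-label share is downward. Section 3.4.7 does not mention it and describes only bias in the opposite direction.

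The size cannot be estimated from the documents and may be close to zero. A reader might take the 4 to 16 point differences in the illustration (24%, 28% and 36% against 20%) as a likely effect. They rest on assumed values of *q* and *f* and support no such conclusion. Nor may one conclude that every patient without a recorded earlier fill was treated outside the label.

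This should be fixed before patients are classified. It does not invalidate the study, since the results are presented as inferred and the rules are still open. The conclusion assumes that the finalized rules keep the current text of Table 5.

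**What to change.** Apply one sequence check across both Rank 1 and Rank 2. Splitting Rank 1 alone would leave order (d), and possibly (b) and (c), on-label through Rank 2.

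1. Count a patient as *Inferred On-label* only if metformin, SU or Lantus was dispensed before the first recorded Byetta script and continued with Byetta. Use all available history, with the 6-month look-back as the minimum. Anchor the check to the patient's first Byetta script on record, not the first in that analysis year.
2. Report patients whose first recorded partner fill is on or after the first Byetta script in a separate row of Tables 6 and 7, *no recorded prior labelled therapy*, outside the on-label count. Show the on-label share with and without this row.
3. State explicitly where patients go whose earlier partner fill had lapsed before Byetta, including those who later resumed it.
4. In section 3.4.7, replace the one-directional statement. Dose and inadequate control are not observed, so on-label use may be overstated. Fills outside the panel may place some patients in the new row wrongly.

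The cost is one date comparison on prescription histories the study already uses, one row per table and some wording. The downside is misplacement from unseen fills. This may be worse for patients who started soon after the June 2011 launch, because the store-consistency criterion applies only after May 2011 and their look-back lies largely before that. Showing the share both ways keeps this visible.

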3.4.7 Limitations

Based on restrictions in Canada, diagnosis can only be inferred. Therefore on-label and off-label use is an estimation based on the applied rules. The off-label use is likely over-estimated as the rules to include a patient in on-label and stringent and all other patients are considered off-label.

Counter indications such as diabetic ketoacidosis, diabetic coma/precoma and end-stage renal failure cannot be inferred from the data source. Therefore, these patients will not be identified in the study.

There is differing amount of information for each patient due to the fixed time frame of the analysis. Since each patient will have a different index date the amount of data will differ for those patients who initiate Byetta at the start of the analysis period compared to patients who initiate Byetta at the end of the analysis

period. This is ensures we have as much data available as possible for each patient so they can be classified appropriately

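### In Table 5 any metformin, sulfonylurea or Lantus overrides overlapping TZD or non-glargine insulin use; taken alone, this ranking can only lower the primary off-label percentage

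*Protocol*

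**What the plan says.** Protocol section 3.4.4 defines the outcome: "The primary outcome of interest is the off label use of Byetta in Canada". Table 5 sorts patients by ten ranked rules, and the ranking decides conflicts: "Therefore patients will be classified based on the highest rank business rule".

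Only the first two ranks are on-label.
- Rank 1: "Concomitant use of* Byetta with metformin (met) and/or sulfonylurea (SU), OR Concomitant use of Byetta with Lantus".
- Rank 2 is for patients in whom "Met and/or SU or Lantus is not prescribed with Byetta, but both appear in the analysis period". The footnote to Table 5 widens this kind of evidence to the whole study period, including look-back and follow-up.

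The rules for Levemir (rank 3), human basal insulin (rank 4), TZD (rank 5) and all other insulin (rank 7) come after these. The text gives an example: "if a patient receives scripts for both Metformin and other insulin during the analysis period, they will be classified as" inferred on-label.

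Section 3.4.4 says that the rules follow the monograph in Table 1. That table names metformin and/or sulfonylurea, or insulin glargine with or without metformin. The regulator's request in section 3.1 reads in part: "Since preliminary information has already indicated off label use of exenatide with either TZD or insulin in the EU". The secondary objective in section 3.2.2 is: "To assess the concomitant use of exenatide with either thiazolidinediones (TZDs) or insulin". On bias, section 3.4.7 states: "The off-label use is likely over-estimated as the rules to include a patient in on-label and stringent".

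**The concern.** The study was requested because exenatide was already being used with TZDs or insulin. Table 5 itself labels Levemir and TZD use as off-label, yet the same exposure becomes on-label once metformin, a sulfonylurea or Lantus (a partner drug, below) is also found. Nothing in Table 1 supports that change of label; it comes only from the order of the rules.

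At stake is the primary percentage in Table 6. It would leave out much of the use that the regulator asked about, while section 3.4.7 tells the reader that the error probably runs the other way.

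**Working it through.** **1. What the ranking does.** Neither on-label rank requires that a TZD or another insulin be absent. Ranks 3, 4, 5 and 7 are therefore reached only by patients with no metformin, no sulfonylurea and no Lantus. Under rank 2 with its footnote, a metformin script from the look-back period is enough to override a TZD taken together with Byetta.

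**2. Check on all drug patterns.** Code Table 5 as a first-match rule over eight drug groups in adults, each present or absent: metformin, sulfonylurea, Lantus, Levemir, human basal insulin, TZD, other insulin, other oral agents. That gives 2^8 = 256 patterns. The code reproduces the protocol's example (metformin plus other insulin is on-label).

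| Patterns containing | Number | Classed on-label |
|---|---|---|
| TZD | 128 | 112 |
| Non-glargine insulin | 224 | 196 |
| Either | 240 | 210 (210/240 = 87.5%) |

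These are counts of possible patterns, not of patients.

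**3. Effect on the percentage.** Let p be the share of patients with any partner drug, and q the share of those who also have a TZD or non-glargine insulin overlapping Byetta. The documents give neither, so both are assumed.

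- Reported off-label share = 1 − p.
- Share with the overlapping users moved out of on-label = 1 − p + p×q.
- Difference = p×q, which cannot be negative.

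| p | Reported | q = 0.05 | q = 0.10 | q = 0.20 | q = 0.30 |
|---|---|---|---|---|---|
| 0.70 | 30% | 33.5% | 37% | 44% | 51% |
| 0.80 | 20% | 24% | 28% | 36% | 44% |
| 0.90 | 10% | 14.5% | 19% | 28% | 37% |

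For example, with p = 0.80 and q = 0.05: 0.20 + 0.80×0.05 = 0.24.

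**4. The other direction.** Section 3.3 gives about 75% coverage (74.6% in Table 2). Under the present rules the on/off split depends only on whether a partner drug is seen. A partner fill at a store outside the panel can therefore only move a patient from on-label to off-label, which pushes the percentage up. The size of that effect is not given either.

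**5. What Table 7 recovers.** It has a TZD row, an insulin row, a column for all patients over 17 and an on-label column. TZD use among patients labelled on-label can be read there. The insulin row, as shown, does not separate glargine from other insulin, so the non-glargine use cannot be recovered from it. Table 6 is unaffected.

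**The case against.** Four points stand on the other side.

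- **Net direction.** A reader might infer that the reported figure is too low overall. The documents do not support that: unseen partner fills act upward, and section 3.4.7 also notes that everyone not meeting the on-label rules defaults to off-label. Its conclusion is not shown to be false overall. What fails is its reason, because rules that any one partner drug can satisfy, even without overlap, are not stringent.
- **Visibility.** A reader might infer that these patients disappear into the on-label group. They do not: the all-patients column of Table 7 reports TZD and insulin use whatever the label, so the TZD part of the secondary objective is served. The gap is the unsplit insulin row and Table 6.
- **Meaning of the label.** The regulator's remark concerns use in the EU, and Table 1 does not expressly address a third agent added to metformin. Treating such use as outside the indication is a reasonable reading, not a proven one. The protocol still has to reconcile its passages, since it claims alignment with Table 1 and labels TZD and Levemir use off-label itself.
- **Draft status.** The rules are to be finalised at study start. That makes the change timely but does not justify the ranking.

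Reversing the order of Table 5 would not be enough. The off-label rules accept evidence from any time, so a patient who stopped a TZD before starting Byetta with metformin would become off-label, an error in the opposite direction.

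**Conclusion.** The point holds for the ranking itself. Table 5 counts overlapping TZD or non-glargine insulin use as on-label whenever a partner drug appears, and this rule alone can only lower the primary off-label percentage, by p×q. The direction of this component follows from the rules; the net bias over all sources is unknown.

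The size is illustrative only. The move from 20% to between 24% and 44% rests on an assumed p of 0.80 and an assumed q of 0.05 to 0.30, with q limited to overlapping use. It covers TZDs and non-glargine insulin only, not other added agents, and not patients who would leave on-label because their partner drug never overlapped Byetta. It should not be read as an estimate for Canada. Because this component bears on the primary outcome, and on the very combinations that prompted the study, it should be corrected before the rules are finalised.

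**What to change.** Reconcile Table 5 with Table 1; which combinations count as on-label is for the sponsor to settle and state. For the analysis:

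1. Apply flags for TZD and for non-glargine insulin before ranks 1 and 2. Base them on the protocol's definition of concomitant use, not on evidence at any time.
2. Require the same overlap for the partner drug that makes a patient on-label.
3. State how other added agents in Table 4 (DPP4, PPG regulators, Prandase, Victoza) are classed.
4. Report the present hierarchy as a secondary result, named as any partner drug.
5. Split the insulin row of Table 7 into glargine and other insulin.
6. Replace the over-estimation sentence in section 3.4.7. For results under the present hierarchy it should say that the partner-drug rules bias off-label use down, unseen fills bias it up, and the net direction is unknown. For the revised rules, add that unseen TZD or insulin fills can also bias it down.

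The cost is modest: the same extract, plus programming of overlap. The off-label percentage may look less favourable. Requiring overlap for the partner drug makes the result more sensitive to unseen fills, which is a reason to keep the secondary result beside it.
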